**Table 3 - Rescue criteria**

Time in study	Threshold
From Randomization up through the scheduled Week 8 visit (Visit 6)	FPG >15.0 mmol/L (>270 mg/dL)
After the Week 8 visit up through the scheduled Week 12 visit (Visit 7)	FPG >13.3 mmol/L (>240 mg/dL)
After the Week 12 visit (Visit 7) through the end of the 30-week Core Treatment Period	FPG >11.1 mmol/L (>200 mg/dL) or HbA1c $\geq$ 8.0%
After the Week 30 visit (Visit 10) through the end of the treatment period (Week 56 [Visit 14])	FPG >8.9 mmol/L (>160 mg/dL) or HbA1c $\geq$ 7.0%

FPG fasting plasma glucose; HbA1c hemoglobin A1c

Routine fasting SMPG and central laboratory alerts on FPG (and HbA1c at Week 12 [Visit 7] onward) are set up to ensure that glycemic parameter results remain below the predefined thresholds.

- If 1 fasting SMPG value exceeds the specific glycemic limit on 1 day, the participant checks it again during the 2 following days. If all the values in 3 consecutive days exceed the specific limit, the participant should contact the Investigator and a central laboratory FPG measurement (and HbA1c at Week 12 [Visit 7] onward) be performed as soon as possible for confirmation
- Upon receipt of a central laboratory rescue alert, a central laboratory re-test must be completed and confirmed as exceeding the threshold for rescue before rescue therapy is initiated. The re-test confirmation should be performed as soon as possible by unscheduled visit

In the event that a confirmatory FPG and/or HbA1c exceed the threshold, the Investigator should ensure that no reasonable explanation exists for insufficient glucose control and in particular that:

- The increased FPG has been tested at a fasted state (ie, no food intake or liquid intake [except water] for  $\geq$ 8 hours)
- IMP was appropriately injected (as per weekly schedule)
- There was no intercurrent disease, which may jeopardize glycemic control (eg, infectious disease)

- Compliance to treatment was appropriate
- Compliance to diet and lifestyle was appropriate

If any of the above mentioned reasons can reasonably explain the insufficient glycemic control, the Investigator should consider not initiating rescue medication and should undertake appropriate action, ie:

- Assess FPG (ie, after  $\geq 8$  hours fast)
- Initiate an evaluation and treatment of intercurrent disease (to be reported in AE/concomitant medication parts of the electronic Case Report Form [e-CRF] and the medical record)

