2.2 DISPOSITION OF PARTICIPANTS

This section describes participants' disposition for both participant study status and the participant analysis populations.

Screened participants are defined as any participants who signed the informed consent form.

Randomized participants consist of all participants with a signed informed consent form who have had a treatment kit number allocated and recorded in the IRT database, regardless of whether the treatment kit was used.

The total number of participants in each of the following categories will be presented in the clinical study report using a flowchart diagram or summary table:

- Screened participants;
- Screen failure participants and reasons for screen failure;

- Nonrandomized but treated participants;
- Randomized participants;
- Randomized but not treated participants;
- Randomized and treated participants;
- Participants who have completed the 30-week core treatment period as per protocol;
- Participants who did not complete the 30-week core treatment period, and main reasons for permanently treatment discontinuation;
- Participants who have completed the whole study treatment period including the 26-week extension period as per protocol;
- Participants who did not complete the whole study treatment period, and main reason for permanent treatment discontinuation;
- Participants who completed the study as per protocol;
- Participants who discontinued the study by main reason for permanent study discontinuation;
- Status at last study contact.

For all categories of participants (except for the screened, screen failure and nonrandomized but treated categories) percentages will be calculated using the number of randomized participants as the denominator. Reasons for treatment and study discontinuation will be supplied in tables giving numbers and percentages by treatment group. Number and percent of participants: screened, screen failed, randomized, randomized and treatment, ended treatment prematurely, and ended study prematurely will be provided by treatment group within each country and site as applicable.

List of participants who discontinued treatment and/or study will be provided with reasons for discontinuation, including reasons related to COVID-19.

Kaplan-Meier cumulative incidence of early IMP, premature discontinuation of treatment due to AE and study discontinuation will be provided.

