In this analysis, missing endpoint values will be imputed 10 000 times to generate 10 000 data sets with complete data. The completed data sets will be analyzed using an ANCOVA model with the treatment group (efpeglenatide 2, 4, or 6 mg, or placebo), randomization stratum of Screening HbA1c ($<8.0, \geq 8.0\%$), BMI at Visit 3 ($<30, \geq 30 \text{ kg/m}^2$), and geographical region as fixed classification effects, and Baseline HbA1c value as a continuous covariate.

For subjects with missing efficacy endpoint data at Baseline, values will be imputed using the population mean at Baseline.

SAS pseudo-codes are provided in [Appendix A](#).

The results from the 10 000 analyses will be combined using Rubin's formula, to provide the adjusted mean change in HbA1c from Baseline to Week 30 (regardless of treatment discontinuation or initiation of rescue therapy) for each treatment group, as well as the difference between each efpeglenatide dose and placebo and the 95% confidence interval (CI) for the difference. This will be implemented using MIANALYZE procedure in SAS.

A hierarchical procedure will be applied to adjust for the multiplicity of comparison on the primary endpoint:

- First, the highest dose of efpeglenatide (6 mg) will be compared to placebo to demonstrate superiority of this dose to placebo
- If superiority is demonstrated for efpeglenatide 6 mg, the superiority of 4 mg dose of efpeglenatide to placebo will be tested
- If superiority is also demonstrated for 4 mg dose, the lowest dose (2 mg) will be tested for superiority to placebo

When the superiority is not obtained in a step, the sequential testing procedure will be stopped.

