As noted, the number of retrieved dropouts is expected to be small, and there may not have sufficient data to support the imputation approach in item 1 described above. If there are less than 5 participants in any arms who prematurely discontinue the study treatment before the endpoint visit but have the measurement for the endpoint, a back-up imputation method for the primary efficacy analysis will be used. In particular, missing endpoint data in all participants in both efpeglenatide and placebo groups, regardless of staying on the study treatment or not, will be imputed using a model estimated from participants in the placebo group with endpoint data without including any intermediate values, where randomization strata and corresponding baseline values are included as the predictors. Missing data will be imputed using the regression method.

Sensitivity Analysis

Tipping point analysis

Tipping point analysis based on the same multiple imputation (MI) method as applied above will be performed to examine the robustness of the results from the primary analysis. A penalty δ will be applied to participants in the efpeglenatide group who have no HbA1C data at Week 30. The penalty will be gradually increased to determine at which level (if any) the conclusion of the

analyses in terms of statistical significance is changed for each efpeglenatide dose group. The tipping point is the penalty level at which the magnitude of efficacy reduction in participants without HbA1c data at Week 30 creates a shift in the treatment effect of efpeglenatide from being statistically significantly better than placebo to a non-statistically significant effect. The penalty δ will start at 0 and increase by 0.1 (unit: %) until non-statistical significance is found. Least square mean difference between each efpeglenatide dose and placebo and its associated p-value will be provided for each penalty level.

Analysis on completers

For participants in ITT population who completed the 30-week core treatment period and did not start any rescue therapy before the end of the period, the primary endpoint will be assessed too by the same ANCOVA model as used for the primary analysis using the observed values.

Assessment of missing data

The availability of primary and secondary efficacy data (yes, no) at the endpoint visit (Week 30 or Week 56) will be summarized by treatment status (discontinued, completed) and by treatment group.

Assessment of treatment effect by subgroup

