2.4.4.2.1 HbA1c $<7.0\%$ at Week 30 (yes/no)

Proportions of participants achieving the HbA1c target value of $<7.0\%$ at Week 30 will be compared by treatment group using a Cochran-Mantel-Haenszel (CMH) test stratified by randomization stratum of Screening HbA1c ($<8.0, \geq 8.0\%$) and Visit 3 (Baseline, Day 1) BMI ($<30, \geq 30 \text{ kg/m}^2$) in the ITT population. All HbA1c values at Week 30 will be used to determine whether a participant is a responder (HbA1c $<7.0\%$) or not, even if they are measured after IMP discontinuation or introduction of rescue therapy. Participants with missing HbA1c data at Week 30 will be considered not achieving HbA1c $<7.0\%$. The nominal p-value from the CMH test will be presented. No rounding for HbA1c will be done.

2.4.4.2.2 Changes from baseline in FPG to Week 30 and in body weight to Weeks 30 and 56 and in HbA1c to Week 56

Changes from Baseline in FPG to Week 30, in body weight to Weeks 30 and 56 and in HbA1c to Week 56 will each be analyzed by the same ANCOVA model with missing values imputed by MI method as described in [Section 2.4.4.1](#) the primary analysis. The least squares (LS) means, standard errors of LS means within each treatment group and the adjusted mean and associated two-sided 95% CI of the difference between efpeglenatide 2, 4, and 6 mg and placebo group will be presented.

Summary statistics at protocol scheduled visits and for the last on-treatment value will also be provided for FPG and body weight.

Additional Analysis

Analysis on completers at Week 30 (body weight)

For participants in ITT population who completed the 30-week core treatment period and did not start any rescue therapy before the end of the period, the secondary endpoint of change from Baseline in body weight to Weeks 30, will be assessed too by the same ANCOVA model as used for the primary analysis using the observed values.

Analysis on completers at Week 56 (HbA1c and body weight)

For participants in ITT population who completed the whole on-treatment period and did not start any rescue therapy before the end of the period, the change from Baseline in HbA1c and body weight to Weeks 56, will be assessed by the same ANCOVA model as used for the primary analysis using the observed values.

Sensitivity analysis due to COVID-19 at Week 56 (HbA1c and body weight)

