Proportions of participants who used rescue therapy during the treatment period until Week 30 and Week 56 will be compared by treatment group using a CMH test stratified by the randomization stratum of Screening HbA1c ($<8.0, \geq 8.0\%$) and Visit 3 (Baseline, Day 1) BMI ($<30, \geq 30 \text{ kg/m}^2$) in ITT population.

Time to initiation of rescue therapy (weeks)

Time to initiation of rescue therapy is defined as the time from the date of randomization to the date of first rescue therapy in weeks. Participants who did not take any rescue therapy during the study will be censored at the date of study completion/discontinuation. The curve of the cumulative incidence of participants with rescue initiation will be estimated using Kaplan-Meier method by study treatment group.

Patient reported outcome

The Patient Qualitative Assessment of Treatment version 2 (PQATv2) is intended for the collection of participant-perceived benefit-risk of glucose-lowering treatment with efpeglenatide. The participants will be asked to complete it from home just before the on-site visits planned at Weeks 30 and 56. If a participant discontinues treatment with IMP during the treatment period, the participant will be asked to complete the PQATv2 at the time of discontinuation.

The analysis of participant-reported outcome (PRO) endpoints will be descriptive with no formal testing. For categorical data, frequency and percentage will be provided by treatment group and overall at scheduled visits. Participants' answers to the open-ended questions of PQATv2 (items #1, 3 and 5) will be analyzed qualitatively and quantitatively, as relevant, using appropriate data analysis software. The analysis method for the open-ended questions will be provided in a separately and the analyses results will not be included in the CSR.

Other exploratory analysis

- Analysis to investigate whether the HbA1c decrease depends on the decrease in weight will be assessed by scatter plots of HbA1c reduction versus weight loss. A cumulative distribution plot will be provided for each of changes in HbA1c and in body weight from Baseline to Week 30 and 56.
- Proportion of participants with HbA1c <7.0% at Week 30 and 56 with no severe or documented symptomatic hypoglycemia will be assessed by number of participants and percentage by treatment group.

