The scheduled measurements at the endpoint visit (Week 30 or Week 56) as collected will be used in the efficacy analyses including those obtained after IMP discontinuation and/or introduction of rescue therapy. For participants whose efficacy measurement is not available at the endpoint visit, the measurement at unscheduled visit (including the end of treatment and/or study visit for those prematurely discontinued) will be used if the unscheduled measurement is within +/-30 days (7 days for FPG and SMPG) of the date of the end point visit [targeted study Day 210 for Week 30 (or Day 392 for Week 56)]. If multiple measurements are associated to the same targeted date, the closest to the targeted study day will be used. In case of equality, the last measurement will be used. If there are still no measurement for a given parameter at an endpoint visit, the data is considered missing for efficacy analyses, where multiple imputation would be applied as appropriately as described in [Section 2.4.4.1](#).

Linked adverse events that worsened or became serious

An AE that worsened or became serious will have a separate record in the data from the original event record with a reference identification number that links the new record to the original record. An AE that worsened or became serious will be considered a new recurring AE in the summary of recurrent events or in the summary of events by time intervals.

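### Does listing the Week 30 HbA1c completer analysis under Sensitivity Analysis call for a change to the SAP?

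*SAP*

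**What the plan says.** The primary analysis of Week 30 HbA1c (SAP 2.4.4.1) estimates the effect "regardless of treatment discontinuation or initiation of rescue therapy"; protocol Table 5 calls this the ITT estimand.

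Under Sensitivity Analysis the SAP then gives two items. The first is the tipping point, which "will be performed to examine the robustness of the results from the primary analysis". The second fits the primary ANCOVA to observed values in ITT participants "who completed the 30-week core treatment period and did not start any rescue therapy before the end of the period". That second item carries no statement of purpose.

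SAP 2.4.4.2.2 has the same kind of analysis for Week 30 body weight, and for Week 56 HbA1c and body weight in participants "who completed the whole on-treatment period and did not start any rescue therapy before the end of the period". There the heading is Additional Analysis.

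No completer analysis appears in the hierarchy of SAP 2.4.4.3. The two conditions that define the subset are each reported by arm. SAP 2.2 tabulates "Participants who did not complete the 30-week core treatment period, and main reasons for permanently treatment discontinuation", and SAP 2.4.4.4 states: "Proportions of participants who used rescue therapy during the treatment period until Week 30 and Week 56 will be compared by treatment group".

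**The concern.** A sensitivity analysis should keep the question of the primary analysis and vary its assumptions. This one changes the population and the question. Rescue follows post-randomisation glucose or HbA1c: the Table 3 row for the period "After the Week 12 visit (Visit 7) through the end of the 30-week Core Treatment Period" uses FPG above 11.1 mmol/L or HbA1c of at least 8.0%. Treatment lowers both, so the arms lose different participants, and adjusting for baseline does not restore comparability. The result is neither the treatment-policy effect nor a no-rescue effect in everyone randomised.

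The placement matters more because the heading has become thinner. The protocol listed the tipping point and a control-based imputation, both keeping the ITT set, and no completer analysis. SAP version 3 removed the control-based imputation. A reader could now take the completer result as half of the robustness evidence, and could call a sound positive result fragile, or a doubtful one confirmed, because of selection. The plan also names no table giving the number per arm who meet both conditions together.

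**Working it through.** **1. The plan's own figure.** Inputs from SAP 1.3: 100 per arm, SD 1.1, two-sided alpha 0.05. SE = 1.1 × √(2/100) = 0.1556.

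- At 0.5: 0.5/0.1556 − 1.96 = 1.254, power 89.5%.
- At 0.6: 0.6/0.1556 − 1.96 = 1.897, power 97.1%.

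The SAP states 89% and 96%, so the design figures reproduce to within about one point. The label enters none of them.

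**2. Smaller subset, no bias.** The same formula at a difference of 0.5, with 90, 80, 70 or 60 completers per arm, gives power of 86%, 82%, 77% or 70%. A completer test loses significance more often even with no selection effect.

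**3. Selection by rescue at Week 30.** The documents give no rescue rates, so all of the following is assumed: baseline HbA1c 7–10% (mean 8.15), placebo change −0.1, no-rescue difference −0.6, SD of change 1.1, between-visit correlation 0.75, fasting glucose 170 mg/dL at HbA1c 8%, rescue lowering HbA1c by 0.7, Table 3 thresholds, and a Week 12 HbA1c able to trigger rescue. Uptake is the share of triggered participants who actually start rescue; in this table it is a stable tendency of the participant.

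| Uptake | 100% | 75% | 50% | 25% |
|---|---|---|---|---|
| Completers | −0.35 | −0.51 | −0.57 | −0.59 |
| Treatment-policy | −0.47 | −0.50 | −0.53 | −0.56 |
| Completers minus treatment-policy | +0.12 | −0.01 | −0.04 | −0.03 |
| Kept, placebo vs active | 44 vs 63% | 58 vs 72% | 72 vs 81% | 86 vs 91% |
| Completers non-significant when treatment-policy significant | 45% | 16% | 5% | 1% |

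The last row comes from 250 simulated trials per setting, which also had 10% random discontinuation.

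- If uptake is redrawn at each trigger, the gaps are +0.12/+0.07/+0.01/−0.01.
- If a Week 12 HbA1c cannot trigger rescue (Table 3 starts the HbA1c criterion after that visit; protocol 6.3.1 sends HbA1c alerts from that visit onward), the gaps with stable uptake are +0.05/+0.01/0.00/−0.01.
- Varying the correlation (0.6–0.85), glucose at HbA1c 8% (150–190) and rescue effect (0.5–1.0), the gap runs from +0.02 to +0.20 at 100%, −0.09 to +0.14 at 75%, −0.08 to +0.06 at 50% and −0.06 to +0.01 at 25%.

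**4. Where the discordance comes from.** At 75% stable uptake the point estimates are almost equal, so the 16% is not attenuation. With 58 and 72 kept, the 95% half-width is 1.96 × 1.1 × √(1/58 + 1/72) = 0.38. With 100 per arm it is 1.96 × 0.1556 = 0.30. The discordance is lost precision, visible from N and the interval. Attenuation matters only near 100% uptake.

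**5. The other direction.** Suppose there is no true effect and poor responders stop in the active arm only. If 13% leave (86.6 kept), the completer difference is −0.131, SE = 1.1 × √(1/100 + 1/86.6) = 0.161, and a nominal 5% test rejects about 13% of the time. If 24% leave, the difference is −0.22 and it rejects about 27% of the time. The completer result is therefore not evidence for or against the primary, whatever its heading.

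**6. Week 56.** Completers give −0.25/−0.66/−0.65/−0.62 against treatment-policy −0.51/−0.53/−0.56/−0.58 (stable uptake). Gaps are larger here, but this version already sits under Additional Analysis.

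**The case for a change.** The best case for a change is that it is nearly free: move one heading to match SAP 2.4.4.2.2, call the analysis supplementary, and add a row with the number retained per arm. The SAP is inconsistent in its own labels, nothing in it warns of the selection, and agreement at 75% stable uptake (−0.51 and −0.50 against a no-rescue effect of −0.60) arises for different reasons in the two analyses.

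Those facts stand; their consequence does not. The plan makes no robustness claim for the completer result. The nesting is inferred from the order of headings, because heading levels are not visible in the text available to me. The protocol's own sensitivity entry also contains descriptive missing-data patterns, so the sponsor uses the heading loosely. The number retained is routine output of a fitted ANCOVA, and its two components are already tabulated. The 45% figure needs every trigger to lead to rescue, whereas protocol 6.1.2.1 requires a confirmatory retest and a search for other explanations, and leaves the start of rescue to the investigator.

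A larger change would add a no-rescue, on-treatment estimand in all randomised participants, imputed under missing at random. That is a trade-off and corrects no error. The assumption is weakest for tolerability-related discontinuation, and protocol 4.3 reports dose-related nausea and vomiting. Week 56 intervals would be wide. It would also need its own rule on whether a pre-rescue value, which under SAP 2.5.4 "will be used if the unscheduled measurement is within +/-30 days", may stand in for the endpoint. The available precision figures allowed that substitution, so they do not describe a version that forbids it.

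**Conclusion.** No change is needed. The heading is loose, and the completer ANCOVA is properly a supplementary analysis of a selected subset, to be read with its N and interval and not as support for the primary. Relabelling it brings no gain: the primary test, alpha, hierarchy, sample size and conclusions are the same either way, and the tipping point, which keeps everyone randomised, remains the stated robustness check.

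In the base-case simulations at uptake of 75% or less, the Week 30 completer estimate differs from treatment-policy by −0.04 to +0.07 HbA1c points; across the wider ranges, by −0.09 to +0.14. These sizes rest on assumed rescue behaviour and on selection by rescue alone. Outcome-related discontinuation could bias the completer result further, as step 5 shows, but would still leave the primary test untouched. The conclusion would differ only if the completer result entered the testing hierarchy or were cited as proof of robustness; the plan does neither.

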2.4.4.2 Analyses of secondary efficacy endpoints

For secondary efficacy endpoints included in the multiplicity procedure described in [Section 2.4.4.3](#), 2-sided statistical tests for the superiority of efpeglenatide to placebo will be performed at the alpha level of 0.05.

